[figure not shown]
CooperVision®

Performance of Avaira Vitality Toric (Fanfilcon A toric) after at least One Month wearing Avaira Toric (Enfilcon A toric)

[figure not shown]
Sponsor Study Code: EX-MKTG-67
Protocol Date: July 2016
Sponsor Company: CooperVision, Inc.
Document Type: Protocol
Study Category: Post Market
Start Date: Sept 2016
Finish Date: March 2017
Clinical Site: Multicenter

Protocol Sponsor:

CooperVision

CRO Centre for Contact Lens Research:

Revision History

Document number	Date	Comments
EX-MKTG-67	8/29/2016	First draft (v 1.0)
EX-MKTG-67	8/31/2016	Second draft (v 2.0)
EX-MKTG-67	9/13/2016	Third draft (v 3.0)

PERSONNEL & FACILITIES

STUDY SPONSOR: CooperVision Inc.
[name]
[name]
USA

[REDACTED]

STUDY INVESTIGATORS: Site A Spokane Eye Clinic
[name]
Site B Hospital Contact Lens Service
[name]
Site C West Village Eyecare
[name]
Site D [name]
[name]

CRO: Centre for Contact Lens Research, Waterloo, Canada
School of Optometry & Vision Science | University of Waterloo
[name] | Canada

Protocol Synopsis

Protocol Number	EX-MKTG-67
Title	Performance of Avaira Vitality Toric Lenses after at least One Month wearing Avaira Toric Lenses
Name of Device(s) and (by USAN material)	Avaira Vitality Toric (Fanfilcon A) Avaira Toric (Enfilcon A)
Indications for Use	
Approved for use:
 
 • Avaira Vitality Toric (Fanfilcon A). (Daily wear) • Avaira Toric (Enfilcon A). (Daily wear) 
Indication for use in this study:
 
 • 1 month of daily wear, each lens
Study Design	Prospective, multi-center, subject-masked, bilateral, daily wear, two-month dispensing study.
Purpose	The aim of this study is to determine if adapted contact lens wearers of Avaira Toric (Enfilcon A) lenses can be confidently refit into Avaira Vitality Toric (Fanfilcon A) lenses and can be successful after one month of daily wear.
Study Duration	
The anticipated timeline for this study is as follows:
 
 • Subject enrolment begins: Sept 2016 • Last subject visit anticipated: Jan 2017 • Visits: 
V1: Screening & optimize prescription for Avaira toric V2: Dispense new or optimized prescription Avaira Toric - this visit may not be necessary if subjects habitually wear optimized power Avaira Toric V3: Baseline Avaira Toric & Avaira Vitality Toric dispense V4: 2 week follow-up wearing Avaira Vitality Toric V5: 1 month follow-up wearing Avaira Vitality Toric & Exit

Patient Population	Habitual toric contact lens wearers that provide written informed consent and meet protocol entry criteria.
Sample Size	Target enrollment of 48 subjects with the hope of at least 44 subjects being in the analysis cohort.
Study Center Location (US)	USA
Number of Centers	Multi-Center, 4 sites.

Patient Follow-up	
Patients enrolled in this study will be followed up after the each lens dispensing session. Follow-ups at:
 
 ○ at least 1 month lens wear of Avaira Toric ○ 2-week and 1 month wear of Avaira Vitality Toric
Primary Endpoints	
 • Visual acuity with contact lenses, • Lens fit performance (centration, rotation, blink movement) • Investigator's fit acceptability
[REDACTED]	[REDACTED]

Table of Contents

1	Introduction	8
2	Study Objective	8
3	Study Hypothesis	8
3.1	Study Hypothesis.....	8
4	Study Design	9
5	Study Population	9
5.1	Sample Size Calculation.....	9
6	Investigational Sites	9
6.1	Number of Sites.....	9
6.2	Investigator Recruitment.....	9
7	Ethics Review / Statement of Compliance	10
7.1	Relevant Standards / Guidelines	10
7.2	Institutional Review Board	10
7.3	Clinical Trial Registration	10
7.4	Informed Consent.....	10
8	Potential Risks and Benefits to Human Subjects	10
9	Materials and Methods	11
9.1	Subjects.....	11
	Inclusion criteria	11
9.2	Study Materials.....	13
9.2.1	Contact lens.....	13
9.2.2	Contact Lens care.....	13
9.2.3	Rewetting/ lubricating eye drops	13
9.2.4	Storage of Study Medications/Treatments	13
9.2.5	Clinical Supply Inventory.....	14
9.2.6	Disposal of Consumables	14
9.2.7	Masking and Control of Study Materials.....	14
9.2.8	Ordering and Accountability of Study Materials.....	14
9.3	Visit Schedule and Procedures.....	14
9.3.1	Visit 1: Screening visit & Establish Optimum Prescription	15
9.3.2	Visit 2: Dispense of Avaira Toric Lens.....	18
9.3.3	Visit 3: Baseline with Avaira Toric & Dispense of Avaira Vitality Toric lenses.....	19
9.3.4	Visit 4: 2-week follow up for Avaira Vitality Toric	21
9.3.5	Visit 5: 1-month follow up on Avaira Vitality Toric Lenses & Study Exit	22

10	Adverse Events and their Reporting	24
10.1	Adverse Response Definitions	24
10.2	Procedures for Adverse Events	26
10.3	Reporting Adverse Events	27
10.4	Discontinuation from the Study	27
11	Statistical Analysis	27
11.1	Statistical analysis	27
12	Data Quality Assurance	28
12.1	Study monitoring	28
12.2	Record keeping	28
12.3	Record retention	28
12.4	Data Entry / Data Management	28
12.5	Confidentiality	29
12.6	Publication	29
13	Study Costs and Subject Compensation	29

1 Introduction

The utilization of soft toric contact lenses has increased significantly over the past few years. CooperVision (CV) produces a number of toric contact lens products including the Avaira toric brand (Enfilcon A) and Avaira Vitality brand (Fanfilcon A). All Enfilcon A toric lenses and Fanfilcon A toric lenses feature CooperVision's exclusive Aquaform® Technology and PEG (Polyethylene Glycol). This combination of material technologies provides a contact lens with high oxygen permeability that is naturally wettable and offers unique comfortable experience.

This study is designed to evaluate how adapted contact lens wearers of Enfilcon A toric lenses will perform following a refit with Fanfilcon A toric lenses, a novel soft contact lens with optimized lens geometry and enhanced water content and UV protection, over one month of daily wear. Overall lens wear experience, including visual quality, lens fit and subjective responses will be assessed.

2 Study Objective

The aim of this study is to determine if adapted contact lens wearers of Enfilcon A toric lenses can be confidently refit into Fanfilcon A toric lenses and be successful after at least one month of daily wear.

Primary outcomes:

- High contrast distance visual acuity (Snellen) with contact lenses
- Lens fit performance (centration, corneal coverage, post blink movement)
- Investigator's fit acceptability

3 Study Hypothesis

3.1 Study Hypothesis

- Null hypothesis (Ho): There is no difference in lens performance between Enfilcon A toric and Fanfilcon A toric lenses for the key variables measured.
- Alternative hypothesis (H1): There is a difference in lens performance between Enfilcon A toric and Fanfilcon A toric lenses for the key variables measured.

4 Study Design

This is a prospective, multi-center, subject-masked, bilateral wear, two month dispensing study comparing the clinical performance of the Fanfilcon A toric lenses following a refit and adaptation with Enfilcon A toric lenses (Table 1). The subjects will be fit bilaterally into the Enfilcon A toric lenses at the first visit (or continue wearing their habitual Enfilcon A toric lenses) which will be worn for a minimum of one month and then subjects will be re-fit bilaterally with a pair of Fanfilcon A toric lenses for another month of daily wear. After the dispensing Fanfilcon A toric lens, subjects will return for follow up evaluations after 2 weeks, and 1 month.

The subjects will be advised that they may be dispensed with either Enfilcon A toric lenses OR Fanfilcon A toric lenses, however all subjects will be refit with Fanfilcon A toric lenses. The participant will not be informed on which study lens he/she is wearing during the second month but the investigator will have this information.

5 Study Population

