5.1 Sample Size Calculation

A sample size calculation was provided based on the 'subjective comfort just before lens removal' (0-10 scale) data on file at CooperVision from study EX-MKTG-63, which gave a standard deviation of 2.4. For an alpha level of 0.05 and power of 0.8, a sample size of 44 will detect a difference of 1.04, which has been confirmed as acceptable by the sponsor.

We recommend dispensing lenses to at least 48 subjects to be sure to have 44 subjects in the eligible analysis population ie. 12/13 at each of the 4 sites.

6 Investigational Sites

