9.1 Subjects

Approximately 48 astigmatic subjects will be enrolled with the aim of at least 44 subjects successfully completing the study and being part of the analysis population. Subjects will either be adapted wearers of Avaira Toric lenses, or they will be refit for a minimum of one month lens wear before being refit to Avaira Vitality Toric. Each subject will be required to attend up to five scheduled study visits over a period of approximately two months.

Each subject will be given a unique ID number. All subjects who sign a consent document will be included in the subject enrollment log which will include; subject ID, date of consent, date of screening, date of study completion, date of discontinuation (if req'd), reason for discontinuation (if req'd). (App 20)

Additionally, all subjects must meet the study inclusion and exclusion criteria listed below.

Inclusion criteria

A person is eligible for inclusion in the study if he/she:

- Is between 18 and 40 years of age (inclusive)
- Has had a self-reported eye exam in the last two years
- Is a habitual soft toric lens wearer
- Can be successfully fit with study lenses (\geq grade 2 fit acceptance)
- Has a contact lens spherical prescription between -1.00 to -6.00D with a cylinder between -0.75 and -1.75D (inclusive)
- Has a spectacle cylinder of at least 0.75D in each eye.

- Can achieve best corrected spectacle refraction distance visual acuity of 20/25 (0.10 logMAR) or better in each eye.
- Can achieve a distance visual acuity of 20/30 (0.18 logMAR) or better in each eye with the study contact lenses.
- Has clear corneas and no active ocular disease
- Has read, understood and signed the information consent letter
- Has a contact lens refraction that fits within the available parameters of the study lenses
- Is willing to comply with the wear schedule (at least 5 days per week, > 8 hours/day assuming there are no contraindications for doing so)
- Is willing to comply with the visit schedule.

Exclusion Criteria

A person will be excluded from the study if he/she:

- Has a history of not achieving comfortable CL wear (5 days per week; > 8 hours/day)
- Presents with clinically significant anterior segment abnormalities
- Presents with ocular or systemic disease or need of medications which might interfere with contact lens wear
- Presents with slit lamp findings that would contraindicate contact lens wear such as:
 - Pathological dry eye or associated findings

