11.1 Statistical analysis

Descriptive statistics will be provided on information regarding baseline variables (e.g., age, gender). Differences between lenses and over time will be compared using Paired t-tests. Paired t-tests

/analysis of variance for normal (interval/continuous) data. The appropriate test will be selected based on tests of normality. Means and standard deviations will be provided for each variable.

A Binomial test will be used to analyze the results for the count data of subjective preferences. The number of "no preference" will be evenly distributed to the two options on the basis they would be equally likely to choose either. All subjects who were evaluated will be used in the analysis. In the event of missing data, individual data points will be excluded in the analysis and not extrapolated from the collected data.

12 Data Quality Assurance

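### The aim is a successful refit at one month, but the plan only tests for a difference between lenses, and non-significance alone cannot show success

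*Combined protocol and SAP*

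**What the plan says.** The Purpose row of the Protocol Synopsis asks whether adapted wearers "can be confidently refit into Avaira Vitality Toric (Fanfilcon A) lenses and can be successful after one month of daily wear". Section 2 repeats the aim: wearers "can be confidently refit into Fanfilcon A toric lenses and be successful after at least one month of daily wear". The primary outcomes in Section 2 are high-contrast Snellen acuity with the lenses, lens fit (centration, corneal coverage, post-blink movement) and the investigator's fit acceptability.

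The null in Section 3.1 is: "There is no difference in lens performance between Enfilcon A toric and Fanfilcon A toric lenses for the key variables measured". The alternative is that a difference exists, in either direction, for key variables that the section does not name.

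Section 11.1 states: "Differences between lenses and over time will be compared using Paired t-tests". It also mentions analysis of variance, a choice of test after checking normality, and a binomial test for preferences. The summary it promises is: "Means and standard deviations will be provided for each variable". For missing data, "individual data points will be excluded in the analysis and not extrapolated from the collected data". It also says that every evaluated subject enters the analysis.

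Section 5.1 sizes the study on comfort before lens removal: "a sample size of 44 will detect a difference of 1.04, which has been confirmed as acceptable by the sponsor".

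The nearest thing to a success standard is a fit-acceptance grade together with an acuity rule, which Section 9.1 gives as: "Can achieve a distance visual acuity of 20/30 (0.18 logMAR) or better in each eye with the study contact lenses". The same pair of conditions governs dispensing at Visits 2 and 3b.

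**The concern.** The favourable answer to the aim, that the new lens does well enough for the refit to count as a success, is close to the null hypothesis, and a test of difference cannot establish its own null. A significant result would have a direction, so a clear loss or gain would inform the aim. A non-significant result could mean that the lenses perform alike or that the data could not tell them apart. Section 11.1 promises no confidence interval to separate these two cases. Means and SDs for each lens do not supply one either, because a paired interval needs the SD of the differences.

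The aim also speaks of success at one month, which is a per-subject result. Acuity and fit acceptance are recorded at Visit 5, but no readable passage says what level counts as success or over which subjects it is counted. At stake is whether the report can answer the study's own question, or whether its readers will take non-significance as the answer.

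**Working it through.** **1. Do the readable criteria serve as a one-month outcome?**
- Section 9.1: fit grade and 20/30 in each eye are conditions of entry.
- Section 9.3.2 (Visit 2): they are conditions for dispensing Enfilcon A.
- Visit 3b: they are conditions for dispensing Fanfilcon A, and a subject without a suitable fit is discontinued.
- Visit 5a: acuity and fit acceptance (0–4) are recorded, with a reason at Grade 2 or less, but no success threshold is attached.

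Every readable use of the criteria as a rule comes before the month of Fanfilcon A wear.

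**2. Reproducing the plan's sample size.** Inputs from Section 5.1: SD 2.4, alpha 0.05, power 0.8, n = 44, difference 1.04. The documents do not say whether 2.4 is the SD of paired differences; take it as such first. For a two-sided paired t-test:
- Standard error = 2.4/√44 = 0.362.
- Noncentrality = 1.04/0.362 = 2.87; critical t on 43 df = 2.017.
- Power = 0.802 (n = 43 gives 0.793). The difference detectable with 80% power is 1.037, which matches 1.04.

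So 44 is correct as the size of a test of difference.

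**3. How often would a real comfort deficit be non-significant at n = 44?** The probability is 1 minus power from the noncentral t distribution, with noncentrality = deficit × √44 / SD of differences. If 2.4 is instead the SD of a single score, the SD of differences is 2.4 × √(2(1 − r)). With r assumed at 0.3 and 0.7 this gives 2.84 and 1.86.

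| True deficit | SD of differences 2.4 | 2.84 (r = 0.3) | 1.86 (r = 0.7) |
|---|---|---|---|
| 0.50 | 72.8% | 79.2% | 58.5% |
| 0.75 | 47.3% | 59.7% | 25.6% |
| 1.04 | 19.8% | 33.9% | 4.8% |

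At SD 2.4 the 95% interval half-width is 2.017 × 0.362 = 0.73 points. This is an illustration only, because comfort is not among the primary outcomes.

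**4. Acuity.** The documents give no SD for the paired acuity difference. With assumed SDs of 0.05, 0.10 and 0.15 logMAR, the half-width 2.017 × SD/√44 is 0.015, 0.030 and 0.046 logMAR. Such intervals may well be informative, so the table above does not carry over to acuity.

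**5. Why the denominator of a success proportion matters.** Section 5.1 expects 48 dispensed and 44 analysed. Suppose 42 subjects succeed (assumed). Exact (Clopper–Pearson) 95% limits:
- 42/44 = 95.5%, interval 84.5% to 99.4%.
- 42/48 = 87.5%, interval 74.8% to 95.3%.
- Best possible case, 44/44: lower limit = 0.025^(1/44) = 92.0%.

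The same 42 successes give figures 8 percentage points apart (95.5 − 87.5), depending only on whether the four subjects without data are counted.

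**The case against.** Several counter-arguments have force.

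- *Imprecision is shown only for a non-primary variable.* This stands. A reader might infer that the study is too small to answer its question on the primary outcomes. The documents do not support that: they give no SD for acuity or fit, and step 4 suggests an acuity interval could be tight. That is a reason to report the interval, since the P value alone does not show its width.
- *One-month information on success exists.* Fit acceptability is a primary outcome graded at Visit 5, with a flag at Grade 2 or less. The Study Forms table also schedules agreement, lens-preference and investigator-preference forms at Visit 5. These bear on a confident refit, but none is stated as a success rule. The two-line acuity check at exit concerns refracted acuity and leads to an explanation or an adverse event form, so it does not measure refit success.
- *A rule may be blacked out.* This is possible: the synopsis row after the primary endpoints and many items at Visits 3 to 5 are hidden. A reader might infer that no success criterion exists anywhere; that cannot be claimed. The objective, hypothesis and analysis sections are readable, however, and they test none.
- *Failed refits are not lost from the record.* This also stands. All evaluated subjects enter the analysis, discontinuations are logged, an exit form is required for every subject ID, and the cohort is discussed before export (Section 12.1). What is missing is a stated denominator.
- *Nothing says that non-significance will be read as success.* Correct. The plan makes no equivalence or non-inferiority claim, and none should be imputed to it. It simply leaves the interpretation of a non-significant result open.

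**Conclusion.** The point holds and should be fixed. The aim is success at one month, while the stated hypotheses and tests address only whether the lenses differ. Followed as written, the plan yields neither a confidence interval for the lens difference nor a one-month success proportion, so a non-significant result would leave the aim unanswered.

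The comfort figures (73% and 47% non-significant at true deficits of 0.50 and 0.75) rest on 2.4 being the SD of paired differences. They illustrate the principle and do not measure the risk for the primary outcomes. The statement about a missing success rule is limited to the readable text. A significant difference would still be informative, and the data remain usable. Nothing here shows that the study is undersized for acuity or that an unsupported claim is planned.

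**What to change.** Amend Sections 3.1 and 11.1 before data export:

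1. Name Visit 5 (Fanfilcon A) versus Visit 3a (Enfilcon A) as the main contrast. Convert Snellen acuity to logMAR, say whether monocular or binocular acuity is used, and report the paired difference with a two-sided 95% confidence interval.
2. Report the proportion meeting the protocol's own fit-acceptance and 20/30 (each eye) criteria at Visit 5, with an exact 95% interval. The denominator should be all subjects in whom the Fanfilcon A refit was attempted at Visit 3b, with those not dispensed counted as not successful. Show the result twice: with subjects lacking Visit 5 data counted as failures, and with them excluded. Before this, reconcile the fit-grade passages: Sections 9.1 and 9.3.2 read ≥ Grade 2, whereas Visit 3b reads > Grade 2, which may be only an artefact of the PDF text.
3. Analyse three-level centration and yes/no corneal coverage with paired categorical methods.
4. State that non-significance alone will not be read as a successful refit.

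No new visits, subjects or measurements are needed. The cost is some extra analysis, possibly wide intervals, and a success figure that may look less favourable: even 44 of 44 has a lower limit of 92.0%. No margin or pass/fail threshold is needed for these changes, and the documents provide no basis for choosing one.

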5.1 Sample Size Calculation

A sample size calculation was provided based on the 'subjective comfort just before lens removal' (0-10 scale) data on file at CooperVision from study EX-MKTG-63, which gave a standard deviation of 2.4. For an alpha level of 0.05 and power of 0.8, a sample size of 44 will detect a difference of 1.04, which has been confirmed as acceptable by the sponsor.

We recommend dispensing lenses to at least 48 subjects to be sure to have 44 subjects in the eligible analysis population ie. 12/13 at each of the 4 sites.

6 Investigational Sites

6.1 Number of Sites

This study design considers 4 sites within the U.S.

6.2 Investigator Recruitment

The principal investigator and co-investigators at each site will be required to fulfil the following criteria:

- Licensed Optometrist or experienced clinician with at least two years of contact lens fitting experience.
- Experienced Investigators who will be trained in Good Clinical Practice (GCP) by the principal investigator.
- In-office email and either document scanning capabilities or fax.
- Willingness to follow the study protocol and to co-operate with the study monitors.

This clinical study is designed to be in conformance with the ethical principles in the Declaration of Helsinki, with the ICH E6 guidelines for Good Clinical Practice (GCP) and all the applicable local guidelines.

7 Ethics Review / Statement of Compliance

7.1 Relevant Standards / Guidelines

This implementation document has been developed in accordance with the following:

- ICH E6- International Conference on Harmonization: Good Clinical Practice (GCP)
- Declaration of Helsinki

7.2 Institutional Review Board

This study will be conducted in accordance with Institutional Review Board regulations (U.S. 21CFR Part 56.103) or applicable IEC regulations. Copies of all IRB/IEC correspondence with the investigator/sponsor will be kept on file. The study will commence upon approval from the following Institutional Review Board: Sterling Institutional Review Board; [contact] and email address: [contact].

7.3 Clinical Trial Registration

This study will be registered with clinicaltrials.gov in accordance with section 801 of the Food and Drug Administration (FDA) Act which mandates the registration of certain clinical trials of drugs and medical devices.

7.4 Informed Consent

Informed consent (App 18) shall be obtained in writing from the subject and the process shall be documented before any procedure specific to the clinical investigation is carried out.

8 Potential Risks and Benefits to Human Subjects

There may be direct benefits to the subjects in this study, such as improved vision and/or comfort. Participation in a study may contribute to scientific research information that may be used in the development of new contact lens products. In addition, subjects will receive an examination of the front part of their eyes and may have the opportunity to try a different type of soft contact lenses and/or different lens care products at no cost to them. The contact lens materials used in this study are commercially available as daily wear. This study will investigate subjects' wearing schedule intended for daily wear (NOT extended wear), similar to the average wearing time of 10-16 hours for daily wear lenses.

This study is considered to be a non-significant risk study based on United States Food and Drug Administration (FDA) and International Standards Organization (ISO) guidelines, because the study devices used as intended in this study (1) do not represent a potential for serious risk to the health, EX-MKTG-67 v.3.0 Performance of Avaira Vitality Toric Lenses after at least One Month wearing Avaira Toric Lenses (Lavender) 13sep2016

safety or welfare of the subject, and (2) are not implants, (3) are not used to support or sustain human life, (4) are not of substantial importance in diagnosing, curing, mitigating or treating disease or otherwise prevents impairment of human health.

Complications that may occur during the wearing of contact lenses include discomfort, dryness, aching or itching eyes, excessive tearing, discharge, hyperemia and variable or blurred vision. More serious risks may include pain, photophobia, iritis, corneal edema or eye infection. Although contact lens-related infections are very infrequent, the possibility does exist. The incidence of infection due to day-wear soft lenses is 0.035%. Almost always an infection will occur only in one eye. This risk is assumed by 35-million Americans who currently wear contact lenses and only current soft lens wearers will be recruited for this study.

Routine clinical procedures including auto-refraction, auto-keratometry, visual acuity, anterior ocular health assessment, and contact lens fitting will be used. In addition, high magnification imaging of the lens fit may be made using 35 mm or digital cameras. Patients will be monitored until the end of the study to reduce the occurrence of adverse or potential adverse events. Patients will be given instructions from their investigator regarding early symptoms and signs of adverse events (also in App 18, Statement of Informed Consent).

9 Materials and Methods

